5.1.1.2 Participant Inclusion Criteria for Healthy Participants (Groups 1A-1C)

Healthy participants eligible to participate in this trial must meet all of the following inclusion criteria:

1. Have the ability to understand the requirements of the study and have provided written informed consent¹ before any study-related procedure is performed.

¹As evidence by signature on an informed consent document approved by the IRB.

2. Agree to abide by the study restrictions.
3. Are healthy male or non-pregnant female, between the ages of 18 and 85 years, inclusive, with normal GFR ≥ 90 at screening.
4. Have no history of chronic tobacco/nicotine usage (i.e., >10 cigarettes per day for 3 months minimum prior to admission).
5. Have a normal QTc interval <460 msec on ECG.
6. Have a BMI of 18 to 40 kg/m² at enrollment.
7. Women of childbearing potential² must use an acceptable contraception method³ for the duration of the study.

²Not sterilized via tubal ligation, bilateral oophorectomy, bilateral salpingectomy, hysterectomy, implanted contraceptive device placement (permanent, non-surgical, non-hormonal sterilization) with documented radiological confirmation test at least 90 days after the procedure, and still menstruating or <1 year has passed since the last menses if menopausal.

³Includes non-male sexual relationships, abstinence from sexual intercourse with a male partner, monogamous relationship with vasectomized partner who has been vasectomized for 180 days or more prior to the participant receiving study product, barrier methods such as condoms with spermicide or diaphragms/cervical caps **with** spermicide, effective intrauterine devices, NuvaRing®, and licensed hormonal methods such as implants, injectables, or oral contraceptives ("the pill").

8. If participant is male and capable of reproduction, agrees to avoid fathering a child for the duration of the study by using an acceptable method of birth control⁴.

⁴In addition to the use of a barrier method (condom) unless vasectomized, acceptable methods of birth control are restricted to a monogamous relationship with a woman who agrees to use acceptable contraception as outlined in inclusion criterion #7, and/or abstinence from sexual intercourse with women.

9. Women of childbearing potential must have a negative urine pregnancy test within 24 hours prior to receipt of study product.

5.1.2 Participant Exclusion Criteria

5.1.2.1 Participant Exclusion Criteria for Patients with Renal Impairment (Groups 2-4)

Participants eligible to participate in this trial must not meet any of the following exclusion criteria:

1. History of known active TB.

2. History of peptic ulcer disease.
3. Known hypersensitivity to pretomanid or any of the excipients.
4. History of any clinically significant uncontrolled cardiac abnormality (as deemed by the PI).
5. Any clinically significant ECG abnormality at screening¹.

¹*Note: the following can be considered not clinically significant:*

- *Heart rate \leq 50 beats per minute (bpm) (sinus bradycardia with heart rate between 45 and 49, inclusive, is acceptable only in younger athletic participants, as determined by the PI)*
- *Mild first-degree atrioventricular (A-V) block (P-R interval >0.23 seconds)*
- *Right or left axis deviation*
- *Incomplete right bundle branch block*
- *Isolated left anterior fascicular block (left anterior hemiblock) in younger athletic participants*

6. History of, or screening results show a QTc interval \geq 460 msec.
7. Family history of Long-QT Syndrome or sudden death when a cause of death is unknown.
8. Inability to swallow tablets.
9. History of fever or documented fever (oral temperature \geq 100.4°F) in the 48 hours prior to admission to the hospital.
10. Resting pulse rate <50 or >110 bpm at Screening.
11. At Screening, blood pressure \geq 20 mm Hg systolic or >10 mm Hg diastolic above baseline² (sitting).

²*Baseline is most recent blood pressure in the last 3 months.*

12. Current hyperkalemia or hypomagnesemia.
13. Positive result of urine drug screen or alcohol screen prior to hospital admission except for approved prescriptions that are not opiates and benzodiazepines.
14. Significant history of drug and/or food allergies (as deemed by the PI).
15. For women, participant is pregnant (positive test for urine Human Chorionic Gonadotropin [HCG]) at screening or Admission, breastfeeding, or planning to conceive for the duration of the study.
16. Any contraindication to the use of nitroimidazoles, or prior treatment with pretomanid or delamanid.
17. Treatment with strong or moderate CYP3A4 inducers or inhibitors³ within 14 days before admission and during the study⁴.

³Except hormonal contraceptives

⁴In the opinion of the site investigator

NOTE: See [Table 4](#) for a list of drugs known to alter the function of CYP3A4 ([Section 7.1.1](#)).

18. Use of St. John's Wort within 7 days prior to admission and during the entire study.
19. Consumption of products containing grapefruit within 5 days prior to dosing until Visit 01N.
20. Donation of whole blood or blood products >500 mL within 30 days from screening and/or plans to donate during the study or up to 14 days after dosing.
21. Participation in another interventional clinical trial within 30 days prior to dosing until after the last study visit.
22. Hgb <8.0 g/dL in both men and women at the screening visit.
23. Positive Screening test for hepatitis C virus (HCV), hepatitis B virus (HBV), or HIV.
24. Renal transplant.
25. Scheduled for hemodialysis or peritoneal dialysis.
26. Presence of any condition or finding⁵ which would jeopardize participant safety, impact study result validity, or diminish the participant's ability to undergo all study procedures and assessments.

⁵In the opinion of the investigator

27. For men, semen donation for the duration of the study.
28. AST and ALT > 2.5 x upper limit of normal (ULN).
29. Hyperbilirubinemia >1.5 x ULN.

5.1.2.2 Participant Exclusion Criteria for Healthy Participants (Groups 1A-1C)

Participants eligible to participate in this trial must not meet any of the following exclusion criteria:

1. History of known active TB.
2. History of peptic ulcer disease.
3. Known hypersensitivity to pretomanid or any of the excipients.
4. History of any clinically significant uncontrolled cardiac abnormality (as deemed by the PI).
5. Any clinically significant ECG abnormality at screening.¹

¹Note: the following can be considered not clinically significant:

- *Heart rate ≤ 50 bpm (sinus bradycardia with heart rate between 45 and 49, inclusive, is acceptable only in younger athletic participants)*
- *Mild first-degree A-V block (P-R interval > 0.23 seconds)*
- *Right or left axis deviation*
- *Incomplete right bundle branch block*
- *Isolated left anterior fascicular block (left anterior hemiblock) in younger athletic participants*

6. Family history of Long-QT Syndrome or sudden death when a cause of death is unknown.
7. Inability to swallow tablets.
8. History of fever or documented fever (oral temperature $\geq 100.4^{\circ}\text{F}$) in the 48 hours prior to admission to the hospital.
9. At Screening blood pressure $> 140/90$ mm Hg or $< 90/65$ mm Hg (sitting).
10. History of, or screening results show a QTc interval ≥ 460 msec.
11. Positive result of urine drug screen or alcohol screen prior to hospital admission except for approved prescriptions that are not opiates and benzodiazepines.
12. Significant history of drug and/or food allergies (as deemed by the PI).
13. Women of childbearing potential with a positive urine pregnancy test within 24 hours prior to receipt of study product.
14. Any contraindication to the use of nitroimidazoles, or prior treatment with pretomanid or delamanid.
15. Treatment with strong or moderate CYP3A4 inducers or inhibitors² within 14 days before admission and during the study³.

²*Except hormonal contraceptives*

³*In the opinion of the site PI*

NOTE: See [Table 4](#) for a list of drugs known to alter the function of CYP3A4 ([Section 7.1.1](#)).

16. Use of St. John's Wort within 7 days prior to admission and during the entire study.
17. Consumption of products containing grapefruit within 5 days prior to dosing until Visit 01N.
18. Donation of whole blood or blood products > 500 mL within 30 days from screening and/or plans to donate during the study or up to 14 days after dosing.
19. Participation in another interventional clinical trial within 30 days prior to dosing until after the last study visit.
20. Hgb < 10.0 g/dL in both men and women at the screening visit.

21. Positive Screening test for HCV, HBV, or HIV.
22. Renal transplant.
23. Presence of any condition or finding⁴ which would jeopardize participant safety, impact study result validity, or diminish the participant's ability to undergo all study procedures and assessments.
- ⁴*In the opinion of the investigator*
24. For men, semen donation for the duration of the study.
25. AST and ALT > ULN.
26. Bilirubin > ULN

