unmetabolized pretomanid is excreted in the urine. [18]. Therefore, like other commonly used anti-TB drugs such as ethambutol and pyrazinamide, which are at least partly eliminated through kidneys, the PK of pretomanid must be studied in patients with CKD. CKD is a very common clinical disease with estimated prevalence of 8 to 16%, and CKD patients globally, particularly those in advanced stages, have significantly increased risk of developing TB [11-13].

Regarding pretomanid metabolites, no single metabolic pathway can be considered major. Two metabolites have been selected for quantification: M19 (4-Trifluoromethoxybenzoic acid) and M50 (hydroxy imidazole). In one mass-balance study, M19 was the largest drug-derived metabolite, representing up to 35% of the sample radioactivity at 24 hours post-dose. However, it has no activity or toxicity. In another mass-balance study, M50 was found to account for 6.3% of the parent area under the AUC and it has been identified as potentially genotoxic based on an in vitro Ames test. In 2 mouse genotoxicity studies, no genotoxicity was observed up to a 2000 mg/kg dose. In a recently completed carcinogenicity study in transgenic mice with M50 exposure 2-3 times the expected human exposure, no pretomanid-related deaths, tumors, or gross necropsy findings were seen. There is no evidence suggestive of any potential carcinogenic hazard in rat toxicity studies up to 6 months and in monkey toxicity studies up to 9 months. No metabolites have been found to represent more than 13% of the total dose in urine and feces. Therefore, based on results from previous studies and expected excretion in urine, measuring the plasma exposures of pretomanid metabolites (M50 and M19) in this patient population will be valuable.

The results from this study will help determine future dosing and frequency of administration of pretomanid that can be safely used in patients with different stages of renal impairment.

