Drawing blood may cause transient discomfort and fainting. Fainting is usually transient and managed by having the participant lie down and elevate his/her legs. Bruising at the blood draw site may occur but can be prevented or lessened by applying pressure to the blood draw site for a few minutes after the blood is taken. Rarely, drawing blood may cause infection (thrombophlebitis). The use of aseptic (sterile) technique will make infection at the site where blood will be drawn extremely unlikely.

Peripheral Catheter (if needed)

Inserting a peripheral catheter may cause pain, bleeding, hematoma, vein irritation, infiltration, extravasation, phlebitis, air embolism, and/or infection. Use of proper aseptic technique during the insertion provides protection against infection.

Pregnancy

It is unknown if the study drug poses any risks to an unborn child. As such, females of childbearing potential, i.e., women who have started menses, must agree to use an effective method of birth control for the duration of the study ([Section 5.1.1](#)). Males who are sexually active with a female of childbearing potential must agree not to father a child or donate sperm for the duration of the study.

Other Risks

Personal Health Information (PHI)

Participants will be asked to provide PHI. All attempts will be made to keep this PHI confidential within the limits of the law. However, there is a chance that unauthorized persons will see the participants' PHI. All study records will be kept in a locked file cabinet or maintained in a locked room at the participating sites. Electronic files will be password-protected. Only people who are involved in the conduct, oversight, monitoring, or auditing of this trial will be allowed access to the PHI that is collected. Any publications from this trial will use de-identified information. Organizations that may inspect and/or copy research records maintained at the participating site for quality assurance and data analysis include groups such as the local Institutional Review Boards (IRBs), National Institute of Allergy and Infectious Diseases (NIAID), and FDA.

As required by US law, a description of this clinical trial will be available on <https://clinicaltrials.gov/ct2/show/NCT03896750>. This website will not include information that can be used to identify participants. At most, this website will include a summary of the results.

There may be other risks, discomforts, or side effects that are unknown at this time.

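### Breastfeeding is a named exclusion for the renal groups but not for the healthy controls, who take the same dose.

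*Protocol*

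**What the plan says.** Renal participants and healthy controls have separate eligibility lists.

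- **Renal groups 2-4, Protocol 5.1.2.1, exclusion 15.** A woman is ruled out if she is pregnant by urine test "at screening or Admission, breastfeeding, or planning to conceive for the duration of the study". SAP 4.3.2 carries the same wording as item 14 of its renal list.
- **Healthy controls 1A-1C, Protocol 5.1.2.2, exclusion 13.** The corresponding item reads "Women of childbearing potential with a positive urine pregnancy test within 24 hours prior to receipt of study product". SAP 4.3.2 repeats it as item 13 of its control list.
- **Healthy controls, Protocol 5.1.1.2.** Inclusion 3 reads in part "Are healthy male or non-pregnant female, between the ages of 18 and 85 years, inclusive". Inclusion 7 says that women of childbearing potential "must use an acceptable contraception method³ for the duration of the study".
- **Healthy controls, Protocol 5.1.2.2, exclusion 23.** This catch-all covers any condition or finding, in the investigator's opinion, "which would jeopardize participant safety, impact study result validity, or diminish the participant's ability to undergo all study procedures and assessments".

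Protocol 4.3 and SAP 4.4.1 give every participant the same product as one 200 mg oral dose. Protocol 2.3.2 states that recipients gain no direct benefit. On reproductive risk, Protocol 2.3.1 says "It is unknown if the study drug poses any risks to an unborn child", and that females of childbearing potential "must agree to use an effective method of birth control for the duration of the study".

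**The concern.** The reason for keeping a nursing woman out of a single-dose study of this drug is possible exposure of the infant. That reason does not depend on the mother's renal function, so one would expect it to apply equally to both populations. Here it is written for one half of the participants and not for the other, and the SAP copies the difference without comment.

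What is at stake is participant protection, not inference. A healthy breastfeeding woman could be enrolled and dosed without any named criterion being broken. The study would then depend on a site noticing something that the sponsor chose to write down for the renal groups.

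**Working it through.** There is no figure to reproduce. The check is a comparison of the two sets of criteria, followed by a test of whether anything else in the control list closes the gap.

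**Step 1: the lists side by side**

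| Status at entry | Renal groups 2-4 | Healthy controls 1A-1C |
|---|---|---|
| Pregnant | Barred (exclusion 15) | Barred (inclusion 3, exclusion 13) |
| Planning to conceive during the study | Barred by name (exclusion 15) | Not named, but incompatible with inclusion 7 |
| Breastfeeding | Barred by name (exclusion 15) | Not mentioned |
| Semen donation (men) | Barred (exclusion 27) | Barred (exclusion 24) |
| Investigator catch-all | Exclusion 26 | Exclusion 23 |
| Dose | Single 200 mg | Single 200 mg |

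**Step 2: could another control criterion exclude a nursing woman?**

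- Inclusion 3 asks that she be healthy and not pregnant. Breastfeeding is neither an illness nor a pregnancy, so she meets it.
- Inclusion 7 concerns contraception. A nursing woman can comply.
- Exclusion 13 is a pregnancy test result. Hers is negative.
- Exclusion 23 is the only route. Its three grounds are the participant's own safety, the validity of results and the ability to complete procedures. A nursing infant is not clearly any of these. The renal list has the same catch-all and still names breastfeeding, so the catch-all was not relied on there.

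**Step 3: is the difference explained?** No reason appears in either document. Semen donation, another reproductive precaution, was put in both lists, which suggests an omission and not a decision.

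**Step 4: how many could be affected?** Controls are 6 of 12 in Part A and 6 + 6 + 6 = 18 of 36 if Part B runs. They are matched to renal participants by race, gender and age within 10 years (Protocol 3.1), so a nursing control would need a female renal counterpart of similar age. The documents give no expected age or sex distribution, so the number cannot be calculated. It is likely small.

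**Step 5: how long would exposure last?** Protocol 2.1.5.2 gives a half-life of about 18 hours. Participants stay in hospital until the 48-hour sample. Assuming simple first-order decline of the parent drug, the fraction left at discharge is 0.5^(48/18) = 0.5^2.67 ≈ 0.16. This ignores absorption time and the metabolites. The same section reports that most excreted radioactivity is eliminated within 6 to 7 days, so elimination is not complete at discharge.

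**The case against.** The strongest reply is that the gap is narrow and that its consequences are easily overstated. Several stronger readings are tempting, and the documents do not support them.

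- **That women planning to conceive remain eligible as controls.** The phrase is missing from the control list, but inclusion 7 and Protocol 2.3.1 require contraception for the whole study. A woman intending to conceive in that period cannot meet this. It is a difference of wording only.
- **That controls uniquely have nothing to gain.** Protocol 2.3.2 says that no recipient benefits directly, in any group.
- **That the drug is shown to be hazardous to an infant.** Of metabolite M50, Protocol 2.2.1 does say that "it has been identified as potentially genotoxic based on an in vitro Ames test". The same paragraph reports no genotoxicity in two mouse studies up to 2000 mg/kg, no drug-related tumors in transgenic mice at 2-3 times the expected human M50 exposure, and no sign of carcinogenic hazard in rat and monkey toxicity studies. The unknown-risk statement in 2.3.1 concerns an unborn child. Neither document gives data on transfer into milk, so harm is not shown.
- **That sites must enroll anyone who fits the lists.** Section 5 forbids exemptions from criteria and sends eligibility questions to the sponsor's medical officer. It does not oblige a site to enroll.
- **That other one-sided criteria, on potassium, magnesium and resting pulse, undermine the QTcF comparison.** The lists are tailored by population: controls face tighter limits on hemoglobin, transaminases and bilirubin. Controls must also be healthy, with QTc below 460 msec and no clinically significant ECG abnormality. QTcF is only summarized descriptively as change from baseline. Damage to the comparison is not demonstrated.

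Confinement to 48 hours also bears on the size of any exposure, although it is not a bar to breastfeeding.

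The breastfeeding gap itself stands after all of this. Tailoring by population explains limits that vary with renal disease. It does not explain why a nursing infant matters in one group only.

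**Conclusion.** The point holds for breastfeeding alone. As written, the criteria name breastfeeding as a bar in Groups 2-4 and nowhere in Groups 1A-1C. The dose is identical, no participant benefits directly, and no reason is given. Only investigator judgment under exclusion 23 could keep a nursing control out, so here eligible means not excluded by any named criterion. It does not mean certain to be enrolled.

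The number of women concerned is likely small. No endpoint, PK comparison, power statement or sample size is affected. The conclusion assumes that no document outside the protocol and SAP, such as the consent form or the manual of procedures, already covers breastfeeding in controls. Even if one does, the two published lists still differ and should agree.

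**What to change.** Reconcile the two exclusion lists on breastfeeding in Protocol 5.1.2.2 and in the control list of SAP 4.3.2, so that the protection written for Groups 2-4 also applies to Groups 1A-1C. Carrying the full wording of renal exclusion 15 across would also remove the harmless difference on planning to conceive. If the sponsor intended the groups to differ, the protocol should state why.

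The cost is one amended criterion in each document and one screening question. No new test or visit is needed, and at most a few extra screen failures should follow.

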5.2 Withdrawal from the Study or Study Termination

5.2.1 Withdrawal from the Study

Participants may voluntarily withdraw their consent for trial participation at any time and for any reason, without penalty.

A participant may withdraw or be withdrawn from this trial for any of the following reasons:

- Medical disease or condition, or any new clinical finding for which continued participation, in the opinion of the site PI or appropriate sub-investigator, would compromise the safety of the participant, or would interfere with the participant's successful completion of this trial, or would interfere with the evaluation of data.
- Participant no longer meets eligibility criteria (see [Section 5.1](#)).
- As deemed necessary by the site PI or appropriate sub-investigator for noncompliance or other reasons.
- Withdrawal of consent.
- Lost to follow-up (defined as 3 unsuccessful attempts to contact the participant; the methods and dates contact was attempted will be documented).
- Termination of this trial.

A participant who is withdrawn or voluntarily withdraws from the study for any reason, whether related to the study drug or not, after having received the study drug, will be considered an early termination subject. The PI or sub-investigator will make every effort to ensure that early termination

participants who have received the study drug complete the early termination assessments and safety follow-up assessments.

5.2.2 Participant Replacement

Participants who sign the informed consent form (ICF) and receive study product, and subsequently withdraw before the first 24-hour time point will be replaced. All other participants who sign the ICF and receive study product, and subsequently withdraw or are withdrawn or terminated from this study or are lost to follow-up will not be replaced. If participants withdraw, or are withdrawn or terminated from the study, or are lost to follow-up after signing the ICF but before receipt of study product, additional participants may be enrolled for replacement. Participants may be rescreened once. Participants who miss a PK blood draw due to lack of venous access will be replaced. If the healthy matched replaced participant does not match the renally impaired participant, the healthy matched participant will be replaced. If a participant vomits within 2 hours of dosing, the participant will be excluded from the study with a plan to replace or rescreen and admit another time, if necessary.

